The *Stanford Binet Intelligence Scales, 5th Edition* (SB-5)(Roid, 2003) will be used to assess verbal, nonverbal, and overall cognitive abilities and will be administered at the baseline assessment. The SB5 will be used to confirm that the adolescent participant meets the inclusion criteria of a full-scale IQ >70 and will also be used as a predictor in statistical analyses. As noted, this will only be collected at the first baseline time point for both groups.

Baseline, Post-Treatment, and 6-Month Follow-Up:

The *Vineland Adaptive Behavior Scales, 3rd Edition* (Vineland-3)(S. Sparrow et al., 2016) is a well-established standardized measure of adaptive behavior that assesses skills in the Communication, Daily Living Skills, and Socialization domains. The DLS domain is comprised of the Personal, Domestic, and Community subdomains and has items that directly correspond to goals being targeted in the STRW intervention. The Vineland-3 will be used at screening to confirm that the adolescent has deficient DLS (i.e., at least 1 of the 3 DLS subdomain standard scores is at least 15 points or more below full scale IQ). Raw scores and age equivalent scores on the DLS domain and subdomains will be used as a primary outcome measure.

The *Daily Living Skills Goal Attainment Scale (DLS-GAS)(Ruble, McGrew, & Toland, 2012)* will be created for each adolescent based on an in-depth clinical interview completed with the parent that assesses specific skills in all of the goals that will be targeted in the STRW intervention. The DLS targeted in STRW will be explicitly defined for each participant using GAS based on their current skill level. For example, for the targeted skill of laundry, parents will be asked to describe their adolescent's ability to independently separate clothes, use the washing machine and dryer, and fold and put clothes away. An independent clinical research coordinator who will not participate in any aspect of the STRW intervention will develop the DLS-GAS for each adolescent participant and evaluate change in goals on the DLS-GAS at post-treatment and 6-month follow-up assessments. The therapists facilitating the STRW intervention will not have access to the DLS-GAS. The DLS-GAS will be utilized as a primary outcome measure.

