A secure REDCap⁸⁰ database has been built and will be maintained for all measures administered in the current study. The primary analysis will be conducted with an intent-to-treat approach. The primary outcome measures for Objectives 1 and 2 at post-treatment and 6-month follow-up are (1) change in Vineland-3 DLS domain raw score and age equivalent score and (2) change in score on the goals targeted on the DLS-GAS. We will also evaluate the Vineland-3 subdomain raw scores and age equivalent scores. The expectation is that the STRW group will have an increased change in score on both the Vineland-3 and DLS-GAS as compared to the control group. All analyses will be done using SPSS Version 20.0. Univariate statistics such as means, medians, and standard deviations will be computed for each variable to allow for examination of any outliers, variables that are not normally distributed, and heterogeneous variance between groups. The comparability of the two groups in some measured baseline covariates prior to treatment will be assessed using chi-square tests for categorical variables and t-tests for continuous variables. Variables found to be non-normal will be transformed using appropriate functions to confirm with the normality assumptions.

To test Aim 1: Initially a two-sample t-test will be used to test the difference on the change scores in the Vineland-3 DLS domain and GAS (post-treatment and baseline) between the STRW and control groups. Although this is a randomized study it is possible that some of the demographic variables might be differentially distributed between the groups. In this case, the initial analysis will be followed by a general linear regression analysis where cohort will be treated as the main effect and other differentially distributed variables will be added to the model as possible confounders in order to investigate the independent effect of the intervention group on outcome.

To test Aim 2: The within-subject change between post-treatment and 6-month follow-up for each individual receiving the intervention will be calculated and a paired t-test will be conducted to evaluate this change (post-treatment and 6-month follow-up).

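### Aim 1 has three primary scores at post-treatment and no rule saying which one decides, which roughly doubles the chance of a false positive if any one may count

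*Combined protocol and SAP*

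**What the plan says.** The Analyses section (DATA ANALYSIS/METHODS) lists the primary outcomes for post-treatment and for 6 months. It says that they "are (1) change in Vineland-3 DLS domain raw score and age equivalent score and (2) change in score on the goals targeted". Those goals are the ones set with goal attainment scaling. The section then adds "We will also evaluate the Vineland-3 subdomain raw scores and age equivalent scores", which places the subdomains outside the primary set.

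The MEASURES section says something different. On the Vineland-3: "Raw scores and age equivalent scores on the DLS domain and subdomains will be used as a primary outcome measure". On the other instrument: "The DLS-GAS will be utilized as a primary outcome measure".

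The Aim 1 test is described as follows: "Initially a two-sample t-test will be used to test the difference on the change scores in the Vineland-3 DLS domain and GAS". It does not say whether the Vineland-3 domain change is the raw score, the age equivalent, or each in turn.

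The nearest text to a success criterion is in the Analyses section: "The expectation is that the STRW group will have an increased change in score on both the Vineland-3 and DLS-GAS as compared to the control". Aim 1 under PURPOSE OF STUDY likewise joins the Vineland-3 and GAS with an 'and'. No alpha level, sidedness, testing order or multiplicity adjustment is stated anywhere.

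**The concern.** A reader cannot tell which result decides Aim 1. The plan does not say what is concluded if the age equivalent is significant and the raw score is not, or if DLS-GAS succeeds and neither Vineland-3 score does. Any of these could be reported as success on a primary outcome, and the choice could be made after seeing which score worked.

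The raw score and the age equivalent are two scorings of the same Vineland-3 responses. Making both primary adds another chance to succeed and little new information.

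The two sections also disagree on how many primary scores there are at post-treatment. The Analyses section gives three. The Measures section gives nine: the domain and three subdomains in two metrics, plus DLS-GAS.

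**Working it through.** **Inputs from the documents**
- Primary scores for Aim 1 at post-treatment: 3 (Analyses).
- Test: two-sample t-test on change scores, STRW versus control (Analyses).
- Power statement: 80% at effect size 0.71 with 32 per group. Assumed mean gains are 9 and 4 months and the SD is 8.4, for each subdomain age equivalent (Sample Size and Power Calculations).
- Planned enrolment: 35 per arm (STUDY DESIGN).

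**Assumptions, because the documents give no figure**
- Alpha: two-sided 0.05 per test.
- Correlation between the raw score and age equivalent test statistics: 0.90 to 0.99.
- Correlation of each with DLS-GAS: 0 to 0.7.

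**Step 1. Does the alpha assumption fit the plan?** n per group = 2 × (1.96 + 0.84)² / 0.71² = 31.1, rounded up to 32. This is the plan's figure. By the noncentral t distribution, power at 32 per group is 0.798. So 32 corresponds to one test at the full two-sided 0.05, and no alpha appears to have been reserved for further tests. That is an inference, since the plan does not state it.

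**Step 2. Upper bound.** Three independent tests: 1 − 0.95³ = 14.3%. Two scorings of the same responses cannot be independent, so this is only a ceiling. As a simple check, if the two Vineland-3 scores were perfectly correlated and GAS independent, there would be two distinct tests: 1 − 0.95² = 9.75%.

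**Step 3. Correlated tests.** The error rate is 1 − P(all three |Z| ≤ 1.96) for a trivariate normal with no true effect, found by simulation:

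| Raw/age equivalent correlation | GAS correlation | Any false positive, two-sided | Any false positive favouring STRW |
|---|---|---|---|
| 0.90 | 0 | 11.7% | 5.9% |
| 0.90 | 0.7 | 9.9% | 5.0% |
| 0.95 | 0 | 11.1% | 5.6% |
| 0.95 | 0.7 | 9.5% | 4.7% |
| 0.99 | 0 | 10.4% | 5.2% |
| 0.99 | 0.7 | 8.9% | 4.4% |

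The range is 8.9% to 11.7% two-sided against 5%, and 4.4% to 5.9% favouring STRW against 2.5%. The free choice between raw score and age equivalent, taken alone, gives 5.6% to 7.1% two-sided.

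**Step 4. If 'both' were a binding rule.** Suppose DLS-GAS and either Vineland-3 score must each favour STRW significantly. With no effect on either instrument, the false-claim rate is 0.1% to 1.0%. If GAS truly improved and the Vineland-3 did not, it would be at most half of 5.6% to 7.1%, about 3% to 4%. Joint power at 32 per group, taking effect size 0.71 for each test and the normal approximation (0.81 each), is 0.81 × 0.81 ≈ 0.66 if the tests are independent and at most 0.81.

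**Step 5. Power behind any single primary.** The plan's own inputs give (9 − 4) / 8.4 = 0.595, not 0.71. At 0.595, power by the noncentral t is about 65% at 32 per group and 69% at 35. These inputs describe subdomain age equivalents, not the domain score or DLS-GAS.

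**The case against.** **The 'both' sentence is already the rule.** This is the best defence. If binding, it would hold the false-claim rate low (step 4). But it is written as an expectation. It states no conclusion for a split result and does not say which Vineland-3 score has to succeed. It shows that a short clarification could settle the matter, not that the matter is settled.

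**The study is a pilot.** The sample size section says the aim is to examine the differences to be expected. That softens the consequence. Still, Aim 1 concerns effectiveness and predicts significant improvement over control, and the plan quotes 80% and 90% power.

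**The nine-score count rests on one sentence describing an instrument.** This stands in part. The Aim 1 test names only the domain and GAS, so three is the right count for sizing the problem. The Measures sentence remains a conflict to correct.

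**A reader might infer far larger error rates** by counting 6-month results too: six tests, or eighteen with subdomains, giving 26% and 60% under independence. The documents do not support this. The only Aim 2 test described is a paired t-test within STRW from post-treatment to 6 months, where the expectation is that gains are maintained, so significance is not another route to the Aim 1 claim. Aim 2 is worded against control, but that mismatch is a separate matter. Independence is also unattainable for two scorings of the same responses.

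**Half of the two-sided errors favour control.** Correct. For a false STRW claim the relevant range is 4.4% to 5.9%, still about double 2.5%.

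**Conclusion.** The point holds for Aim 1 at post-treatment. Three scores are primary, the Measures section conflicts by adding the subdomains, and nothing written decides between them. If any one may carry the claim, the false positive rate is about 9% to 12% two-sided, or about 4.4% to 5.9% favouring STRW. The error rate is roughly doubled.

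The size depends on an assumed two-sided 0.05 per test and the assumed correlations. The absence of a decision rule does not depend on them.

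**What to change.** In the Analyses section, name one Vineland-3 DLS domain score as the primary outcome: change from baseline to post-treatment, STRW versus control, two-sided 0.05. The age equivalent is a reasonable choice because it is the metric used for the power calculation. Test DLS-GAS at post-treatment second, at the same level, only if the first test is significant. Make the other scoring, the subdomains and the 6-month results secondary. Correct the Vineland-3 and DLS-GAS entries under MEASURES to match.

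Alternatively, make 'both' a binding co-primary rule, name the one Vineland-3 score that must succeed, and state the joint power.

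**Cost.** The change is to wording. Under either option, a success on DLS-GAS alone could not be claimed as primary. In the fixed sequence the first test loses nothing to alpha splitting. By comparison, at effect size 0.71 a Bonferroni split would need 38 per group for two tests or 42 for three. Power for the chosen domain score still has to be restated, because the present figures concern subdomains and the stated inputs do not give 0.71.

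**Timing.** The document is dated 11/23/2022 and the DURATION section has analysis running through December 2022. Cohort 1 is offered only the 24-month call, depending on when participants finished the intervention, so post-treatment data may already exist. If comparative outcomes have been seen, the hierarchy should be labelled post hoc and every listed primary score reported.

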
STUDY DESIGN:

Pilot RCT of Surviving and Thriving in the Real World (STRW): The pilot RCT will consist of running 5 cohorts of 16-20 high functioning adolescents with ASD (IQ≥70) and their parents in a

STRW treatment group or social skills control group. Once an eligible cohort of 16-20 adolescents with ASD has been recruited, adolescents will be randomly assigned to either the STRW group or control group using a stratified randomized block design with IQ as a strata variable (IQ<85 and IQ≥85) to ensure balanced group assignment for each cohort. Approximately 8-10 adolescents with ASD and their parents will participate in each STRW group. Thus, across 5 cohorts, the goal will be to enroll at least a total of 70 adolescents in the study, 35 in the STRW group and 35 in the control group across Years 1-3.

SELECTION AND RECRUITMENT OF PARTICIPANTS:

Inclusion Criteria

The inclusion criteria for the 70 adolescent participants include the following: between the ages of 15-22, in the last 2 years of high school (i.e., in the 11th or 12th grade or has deferred their high school graduation); a diagnosis of ASD (based on clinical judgement and/or meeting the cut-off score on the Autism Diagnostic Observation Schedule, 2nd Edition; ADOS-2)(Lord et al., 2012); a full scale IQ of 70 or above as measured by the Stanford Binet Intelligence Scales, 5th Edition (SB-5)(Roid, 2003); and deficient DLS as assessed by the Vineland Adaptive Behavior Scales, 3rd Edition(S. Sparrow, Cicchetti, & Saulnier, 2016) (Vineland-3; i.e., at least 1 of the 3 Daily Living Skills subdomains is at least 15 points below their full scale IQ).

Exclusion Criteria

Exclusion criteria include significant aggressive behaviors or mental health issues that require treatment out of the scope of the current intervention. Information about medication usage and services/therapies received at home, school, or community will be collected at each assessment. Also, if the adolescent has already completed the social skills group (PEERS), either at Cincinnati Children's or in another setting, they will not be eligible for the study unless it has been a significant amount of time since they did the PEERS group (2-3 years, or up to the discretion of the PI). In these cases, the parent must give verbal understanding that their child may be randomized to the social skills group.

Recruitment

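### Aim 1 is first tested with an unadjusted t-test on change scores, and any adjustment waits on chance imbalance; one pre-specified model adjusting for baseline, IQ stratum and cohort would be clearer and probably more precise

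*Combined protocol and SAP*

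**What the plan says.** The Study Design section randomises each recruited cohort as it fills, five in all, with a "stratified randomized block design with IQ as a strata variable" (below 85, or 85 and above) "to ensure balanced group assignment for each cohort". The goal is "35 in the STRW group and 35 in the control group across Years 1-3".

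The Analyses section, under Aim 1, then plans: "Initially a two-sample t-test will be used to test the difference on the change scores in the Vineland-3 DLS domain and GAS", comparing arms on post-treatment minus baseline. No covariate enters.

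Baseline comparability is screened first: "The comparability of the two groups in some measured baseline covariates prior to treatment will be assessed using chi-square tests for categorical variables", with t-tests for continuous variables. Neither a list of variables nor a cut-off is given. The plan allows that "some of the demographic variables might be differentially distributed between the groups", and continues: "In this case, the initial analysis will be followed by a general linear regression analysis where cohort will be treated as the main effect", with the other imbalanced variables added as possible confounders. The stated purpose is "in order to investigate the independent effect of the intervention group on outcome".

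Two general statements in Measures also bear on this. The Background History Form variables are to serve as covariates, and the SB-5 IQ score as a predictor, in statistical analyses. Neither statement names a model or refers to Aim 1.

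**The concern.** There are three linked weaknesses.

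- **Baseline.** A change score fixes the coefficient on baseline at 1. A linear model estimates it, and under randomisation usually has a smaller residual variance.
- **Design factors.** The allocation is balanced within cohort and IQ stratum, but the test ignores both. If they predict change, the t-test's standard error is too large.
- **Choice of covariates.** Adjustment is triggered by the baseline comparison. Under correct randomisation such differences are chance, and they do not show which variables predict outcome. Stratification makes an IQ imbalance unlikely, so the screen will rarely bring IQ in. If the regression does run, there are two Aim 1 results and no statement of which governs.

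The regression sentence also contradicts itself. In Study Design a cohort is a recruitment wave, yet here it is the main effect in a model meant to isolate the intervention.

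At stake are some power in a trial of about 70 participants and a clear answer to which analysis decides Aim 1.

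**Working it through.** **Inputs from the plan.** Sample Size and Power Calculations, Aim 1, gives mean gains of 9 and 4 months, SD 8.4, a stated effect size of 0.71, 80% power and 32 per group. Study Design gives a goal of 35 per arm, five cohorts and two IQ strata.

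**Assumed, because the documents do not give them.** Two-sided alpha 0.05; correlation rho between baseline and post-treatment scores; ratio k of post to baseline SD; share of change variance explained by IQ stratum and cohort. The power figures refer to subdomain age equivalents. They are borrowed here for the domain test, and nothing in the plan gives figures for the domain raw score or the GAS.

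**Step 1: reproduce the plan's figure.** At d = 0.71, 80% power needs 32 per group by the normal formula and 33 by the t distribution; 32 per group gives 79.8% by t. One-sided 0.05 would need only 25 to 26. The plan's calculation is therefore two-sided and unadjusted.

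**Step 2: note the conflict in its inputs.** (9 − 4)/8.4 = 0.595, not 0.71, while 0.71 × 8.4 = 6.0 months. At d = 0.595, 32 per group gives 65.0%. Both effect sizes are carried forward.

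**Step 3: effect of adjusting for baseline.** The variance ratio, adjusted model to change score, is

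k²(1 − rho²)/(1 + k² − 2·rho·k),

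which is (1 + rho)/2 when k = 1. The effective d is d/√ratio. Noncentral-t power with 32 per arm (62 df unadjusted, 61 adjusted):

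| rho | ratio | d = 0.595: t-test → adjusted | d = 0.71: t-test → adjusted |
|---|---|---|---|
| 0.5 | 0.75 | 65.0% → 77.2% | 79.8% → 89.7% |
| 0.7 | 0.85 | 65.0% → 72.0% | 79.8% → 85.8% |
| 0.8 | 0.90 | 65.0% → 69.5% | 79.8% → 83.8% |
| 0.9 | 0.95 | 65.0% → 67.2% | 79.8% → 81.8% |

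At 35 per arm and d = 0.595: 69.0% → 80.9, 75.9, 73.5 and 71.2%.

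**Step 4: where there is no gain.** With k = 1.25 and rho = 0.8 the ratio is 1.5625 × 0.36/(1 + 1.5625 − 2.0) = 0.5625/0.5625 = 1.00.

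**Step 5: the full model by simulation.** Baseline, IQ stratum and cohort use 1 + 1 + 4 = 6 df. With 20,000 runs per row, 32 per arm and d = 0.595:

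| Situation | t-test | Full model |
|---|---|---|
| rho 0.5, design factors not prognostic | 64.7% | 76.0% |
| rho 0.7, design factors not prognostic | 64.4% | 70.7% |
| rho 0.7, design factors explain 10% | 65.3% | 75.1% |
| rho 0.7, design factors explain 30% | 66.8% | 85.0% |
| rho 0.8, SD ratio 1.25 | 65.2% | 64.0% |
| no covariate prognostic | 65.7% | 64.3% |

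**Step 6: error rates under the null.** The t-test's type I error is about 5%, 4% and 2% when the design factors explain 0, 10 and 30% of variance; the full model holds about 5%. If success were claimed on either the t-test or the triggered regression, with an assumed screen at p < 0.05 on 4 to 10 covariates, the error is 5.1 to 5.8% when the design factors are not prognostic, and 2.4 to 4.9% when they explain 10 to 30%.

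**Step 7: how often the trigger would fire.** With m independent baseline tests at an assumed 5%, the chance of at least one flag is 1 − 0.95^m: 19% for m = 4 and 40% for m = 10.

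**The case against.** The strongest reply is that nothing here is an error. Under randomisation the change-score t-test is unbiased, and its error rate is at or below nominal. The trial is described as a pilot meant to learn what differences to expect. Every input that determines the gain is assumed, and the 85.0% figure needs design factors explaining 30% of change variance, for which the documents offer no support. Baseline Vineland-3 is also an eligibility measure. If that narrows its spread the gain shrinks: with slope 0.7 and baseline variance halved (assumed), adjusted power is 68.6%, not 72.0%. For the GAS, goals are set to each participant's current level, so baseline may carry little information.

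Most of this stands, and it limits the claim. It does not remove it: the plan still states and powers a between-group hypothesis, the data are already collected, and the downside is small.

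Three stronger readings are tempting and are not supported.

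- A reader might infer that the choice of test causes a fall from 80% to 65% power. It does not. That gap is the conflict between 5/8.4 and 0.71 in the power section; at 0.71 the t-test has about its planned power.
- A reader might infer serious error inflation from the two-stage approach. The calculated excess is under 1 point, and the plan does not say the regression can replace the initial test.
- A reader might infer that the plan never intends to use IQ or background variables. Measures says in general terms that it will, but does not connect them to the Aim 1 test.

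**Conclusion.** The point holds as one of efficiency and clarity. The Aim 1 test is valid but leaves baseline, IQ stratum and cohort unused, and the fallback model picks its covariates by chance imbalance and misnames its main effect.

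At 32 per arm with equal SDs, baseline adjustment adds about 2 to 12 points of power at d = 0.595 and 2 to 10 at d = 0.71, for correlations from 0.9 down to 0.5. It adds nothing at SD ratio 1.25 with correlation 0.8, and the full model loses about 1 point if no covariate is prognostic. The direction is likely favourable, but the size cannot be fixed from the documents. The improvement should be made; the t-test result would not be wrong without it.

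**What to change.** - For the Vineland-3 DLS domain, pre-specify one governing linear model: intervention arm as the tested effect; baseline score, IQ stratum and recruitment cohort as covariates.
- Use the same model for the GAS, with a baseline term only if baseline GAS scores vary between participants.
- Drop the selection of covariates by observed imbalance, and keep the t-test as a sensitivity analysis.
- Reword the regression sentence so that arm is tested and cohort is a covariate.
- The document is dated 11/23/2022 and the Duration section has analysis running through December 2022. Record, with a date, that the change preceded any comparison of outcomes by arm; otherwise label the adjusted model post hoc.

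The cost is revised wording and that record. No new data are needed. The six degrees of freedom alone cost about 0.2 points of power (65.0% to 64.8%). Counting chance imbalance as well, the simulated cost when nothing is prognostic is 1.4 points at 32 per arm and 1.1 points at 35 (69.3% to 68.2%).

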We will conduct a phone interview with the parent at 12, 18, and 24 months from the end of the group. We will complete the Vineland-3 Interview, and a short follow-up survey to get current information about the young adult participant. The 12, 18, and 24 month data may or may not be collected based on when a participant completed the intervention. Therefore, Cohort 1 will only do the 24 month visit, Cohort 2 will do 18 and 24 month visit, Cohorts 3-5 will do the 12, 18, and 24 month visit. We will reconsent any family who both 1.) Agrees to complete these time points, and 2.) Signed a previous version of the consent.

Follow Up Outcomes Survey

Parents may complete a one-time 15-20 minute outcomes survey to assess their child's current status in education, work, independent living, social connectedness, and daily living skills after completing the intervention in the last 18-42 months. This will provide us with feedback for the interview we are developing to look at longer-term outcomes after completing the daily living skills intervention.

MEASURES

Electronic administration and scoring will be used when possible for all measures excluding the ADOS-2 and the Stanford Binet 5. The ADOS-2 may be video recorded for training and reliability purposes.

Baseline only:

The **Background History Form** will collect demographics including race, ethnicity, maternal education, household income, and current treatments and services. Information obtained from the

Background History form will be utilized to describe the sample and as covariates in statistical analyses.

The *Autism Diagnostic Observation Schedule, 2nd Edition* (ADOS-2)(Lord et al., 2012) is a well-established clinician-administered diagnostic assessment. Module 4 of the ADOS-2 will be administered to all adolescents at the baseline assessment to confirm ASD diagnosis. [name] is research reliable and a certified trainer of the ADOS-2. In addition to being suited to screen for eligibility, the ADOS-2 will be used to describe the sample and as a predictor in statistical analyses. As noted, this will only be collected at the first baseline time point for both groups.

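### The follow-up Aim 1 regression names cohort as its main effect and lists no treatment term, although its stated purpose is the intervention-group effect

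*Combined protocol and SAP*

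**What the plan says.** The Analyses section (under Data Analysis/Methods) sets out Aim 1 in two steps.

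- **Step 1, always done:** "Initially a two-sample t-test will be used to test the difference on the change scores in the Vineland-3 DLS domain and GAS", comparing STRW with control.
- **Step 2, only if demographic variables differ between the groups:** a general linear regression in which "cohort will be treated as the main effect and other differentially distributed variables will be added to the model as possible confounders". Its purpose is given in the same sentence: "in order to investigate the independent effect of the intervention group on outcome".

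Two other sections show what a cohort is in this trial.

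- **Study Design:** "The pilot RCT will consist of running 5 cohorts of 16-20 high functioning adolescents with ASD". Each cohort is randomised to STRW or control in blocks, "with IQ as a strata variable (IQ<85 and IQ≥85) to ensure balanced group assignment for each cohort".
- **12-Month, 18-Month, and 24-Month Parent Follow-Up:** "Cohort 1 will only do the 24 month visit, Cohort 2 will do 18 and 24 month visit", with a further schedule for Cohorts 3 to 5.

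**The concern.** The regression sentence lists two kinds of term: cohort, and variables found to be imbalanced. Treatment group is neither, yet its effect is what the sentence says the model investigates. The model and its purpose do not match.

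The arms are called groups in the Aim 1 text and in the design section, while cohort is used for the recruitment waves. The terms of the model therefore cannot simply be read as naming the treatment arm.

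At stake is the adjusted Aim 1 estimate, the plan's only stated follow-up when the groups differ at baseline. Its treatment term would have to be supplied by whoever fits the model, possibly after the data have been seen.

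**Working it through.** **1. The plan's own figure.** This point disputes no stated number. For reference, 80% power at effect size 0.71 with 32 per group reproduces: 79.8% by the t-test and 81.1% by the normal approximation. Both assume a two-sided 5% level, which the documents do not state. The illustration below uses the plan's means and SD directly. They give (9 − 4)/8.4 = 0.595 rather than 0.71; that mismatch is a separate matter, but it explains why power below is under 80%.

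**2. The terms side by side.**

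| Element | In the regression sentence |
|---|---|
| Named main effect | Cohort |
| Other listed terms | Imbalanced variables, as possible confounders |
| Treatment group as a model term | Not listed |
| Stated target | Independent effect of the intervention group |

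**3. Why cohort cannot stand in for arm.** If each cohort is split equally, its expected mean change is (9 + 4)/2 = 6.5 months in every cohort, absent true cohort differences. Contrasts between cohorts are then zero whatever the treatment effect. This is exact under perfect balance and approximate with odd cohort sizes or dropout.

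**4. Where the treatment effect goes if the listed model is fitted.** Inputs: 35 per arm in total (Study Design), so 5 cohorts with 7 per arm; difference 5 months and SD 8.4 (Sample Size and Power Calculations). Assumptions: no true cohort effect, no confounders in the model, two-sided 5% level for the arm test.

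- Error variance: 8.4² = 70.56.
- Sum of squares due to arm: 70 × (5/2)² = 437.5.
- Residual degrees of freedom with cohort only: 70 − 5 = 65.
- Expected residual mean square: 70.56 + 437.5/65 = 77.29.
- Expected cohort mean square: 70.56.

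The arm effect falls into the residual, so the cohort F-test (4 and 65 degrees of freedom) rejects below its nominal 5%. The cohort column was obtained by simulation and the arm columns from the noncentral t distribution:

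| Per arm per cohort | True arm difference | Cohort F-test significant | Arm contrast significant | Arm contrast, cohort also in model |
|---|---|---|---|---|
| 7 | 0 months | 5.0% | 5.0% | 5.0% |
| 7 | 5 months | 3.5% | 69.0% | 68.9% |
| 7 | 10 months | 1.2% | 99.8% | 99.8% |
| 8 | 5 months | 3.5% | 74.8% | 74.8% |

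Seven per arm follows from 70/5 = 14 per cohort, below the stated 16–20. Eight per arm is the smallest size within that range.

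In a separate simulation of 2,000 trials with 7 per arm per cohort, a model with group and cohort recovered the treatment difference (mean estimate 4.98 against a true 5).

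**5. The two possible repairs differ.** Take 35 per arm, equal cohorts and exact balance, and let τ² be the variance of true cohort means, which the documents do not give.

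- *Group in place of cohort:* residual degrees of freedom 70 − 2 = 68. Expected residual variance 70.56 + (14 × 4 × τ²)/68 = 70.56 + 0.82τ².
- *Group and cohort:* residual degrees of freedom 70 − 6 = 64. Expected residual variance 70.56.

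Under exact balance and without confounders the point estimate is the same. The standard error is not, once τ² exceeds zero. Cohort differences are plausible: both intervention sections say an undetermined number of sessions moved to telehealth because of COVID-19.

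**The case against.** The strongest defence is that the sentence states its own target. The intervention-group effect cannot be investigated without a group term, so a sensible analyst would supply one. Either cohort is a slip for group, or cohort is an adjusting factor beside the other variables and the tested term is implied. This stands as evidence of intent. It does not settle which model was meant, and no other section does.

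Second, the regression is conditional and follows the t-test rather than replacing it. This stands in full. A reader might infer that the main Aim 1 comparison tests the wrong factor, or that the adjusted result will necessarily be missing or misreported. The documents support neither: the t-test is explicitly between the arms, and the regression sentence names the right target.

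Third, the simulated cohort rejection rates assume that cohorts do not differ, so a rate at or below 5% is built in; the confounders are also left out. This stands too. The figures illustrate that a cohort test says nothing about treatment. They do not estimate harm to this trial.

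Fourth, adding cohort as a blocking factor chooses between the readings. It does, but for a reason found in the design: randomisation was carried out within each cohort, "to ensure balanced group assignment for each cohort".

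**Conclusion.** The point holds as an internal inconsistency in one conditional, follow-up model. As listed, the adjusted Aim 1 regression has no STRW-versus-PEERS term, so it cannot deliver the effect it is said to investigate. Whether a word was mistaken or a term omitted cannot be told from the text.

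This rests on the wording of the regression sentence and on cohort meaning a recruitment wave, as in Study Design and in the long-term follow-up section. It does not rest on the simulation. The unadjusted Aim 1 comparison is unaffected. The matter should be corrected because the present text leaves the adjusted model open to choice after the data are seen, not because the trial's main result is at risk.

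**What to change.** Replace the clause on the main effect with wording such as:

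> *Treatment group (STRW versus PEERS) is the tested term. Recruitment cohort enters as a blocking factor, because randomisation was done within cohort, together with the confounders. The treatment-group coefficient with its 95% CI is the adjusted Aim 1 result.*

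The cost is one sentence and up to 4 degrees of freedom for cohort. With 70 participants and before any confounders, residual degrees of freedom go from 68 to 64; in the illustration above, power falls only from 69.0% to 68.9%. No new data, visits or participants are needed.
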